read to them. We will analyze the talking touchscreen groups and paper-based groups separately. We hypothesize that the talking touchscreen will reduce health literacy-related test bias by level of health literacy, relative to traditional paper-based methods. This will be evidenced by fewer items being flagged for DIF in the group that receives the talking touchscreen. In terms of descriptive statistics to display the magnitude of effects, we will report effect sizes (McFadden's R^2) of DIF items, as well as test characteristic curves (TCCs) for DIF items. Among participants with low health literacy, we expect that the discrimination parameters of the touchscreen condition will be higher than the paper-based condition.

- **Determine the degree of differential item functioning (DIF) of tools relevant to clinical research across different levels of health literacy.** DIF analyses will be conducted to identify test bias by level of health literacy. This will ensure that individuals with low literacy are assessed fairly in clinical and research settings. We will assess a broadly applicable instrument to primary care – the PROMIS Profile, which measures anxiety, depression, fatigue, pain interference, pain intensity, physical function, sleep disturbance, and social roles and activities. Other questionnaires included in the study are shown in Table 1. We will stratify participants into low versus adequate literacy levels using Health LiTT (groups will be formed according to T scores of < 55 vs. 55+).¹⁵ A secondary analysis will use the NUMI, a measure of health numeracy, in three groups (low = 0-3, medium = 4-6, high = 7 or greater). Then, we will determine whether psychometric properties of each questionnaire scale are consistent for individuals with low health literacy versus adequate health literacy. We hypothesize that DIF will be observed for multiple scales using paper-and-pencil administration, suggesting a need to improve test items, and a need to examine alternative ways to administer these tools.

Statistical methodology

Overview

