Data will be summarized by group and in total. In summary tables of continuous variables, the minimum, maximum, mean, and standard deviation will be presented with one decimal place. We will use counts and percentages in table for categorical variables. The denominator for each percentage will be the number of participants within the group unless otherwise specified. All hypothesis testing will be carried out at a two-tailed Type I error rate of $\alpha = .05$ unless otherwise specified. P-values will be rounded to three decimal places with a minimum of < 0.001 in tables. If statistical methods change during analysis, this will be documented in all reports with justification. Additional analyses of these data will be inevitable, but any exploratory analyses will be clearly marked as such.

Statistical power analysis and sample size selection

IRT and DIF analyses require large samples due to the large number of free parameters to be estimated. The proposed sample size herein is larger than other successful implementations of these same analyses carried out in other IRT studies.¹⁶⁻¹⁹ Moreover, we have carried out computer simulations to determine if our proposed sample sizes will be sufficient to create IRT models. We assumed a one-factor model across two groups at $n = 100$ each with standardized factor loadings set to .7 for eight questionnaire items. We used two groups for this simulation to ensure that any pairwise model comparisons would have adequate power. For this simulation, we specified that a non-significant model χ^2 was a good fit, which is a conservative decision because this particular test is highly sensitive relative to other measures of model fit, especially with large samples. Across 500 iterations, a good-fitting model was identified across groups 90% of the time. Even dropping the sample size to as low as $n = 50$ would identify a good-fitting model 84% of the time.

Missing data

We will describe the rate of missing data on an item-by-item basis using frequency tables in R. We do not anticipate high rates of missing data, but we will conduct subgroup analyses by health literacy, site, and administration mode as need to help diagnose any problems with missing data. For DIF analyses, IRT models

Table 1	
Visit 1 (Baseline)	Description of instrument
Language Assessment	To determine testing in English or Spanish
Single Item Health Literacy Screener	To screen for possible literacy status

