PROMIS Profile	To assess health-related quality of life.
PHQ-9	Self-report measure of depression.
Berlin Questionnaire (for sleep)	Self-report measure of sleep quality.
Purpose and Meaning (NIH Toolbox)	Self-report measure of the degree of meaning and purpose a person feels in their life.
RRS	Self-report measure of negative, repetitive thoughts.
PTSD Checklist	Self-report measure of posttraumatic stress disorder symptoms.
*C-SSRS Lifetime	Self-report measure of recent history of suicidal ideation and behavior. (This is not a variable of interest that will be used only to ensure patients' safety).
*C-SSRS Last Contact	Self-report measure of suicidal ideation and behavior since the individual's most recent assessment. (Used only as necessary to ensure patients' safety).
Exit Interview	

are estimated using full-information approaches that use all available data and can accommodate missing responses. We do not foresee a need for an imputation strategy, but if that were to become necessary, we will update this plan accordingly before running any analyses.

Study Design

This is a randomized experiment aimed at determining whether talking touchscreen technology can reduce DIF and provide a better testing experience, relative to paper-based testing. The original study design is shown below in Table 2, although as a result of the COVID-19 pandemic, we were unable to recruit all 1216 participants, but instead collected additional longitudinal data on a subset of participants ($n = 304$)

Table 2: Study Design			
Northwestern		BUMC	

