Each participant will be asked to complete a baseline assessment (Visit 1), three-month follow-up (Visit 2), and a six-month follow-up (Visit 3). Longitudinal data will be analyzed, within language and within mode of administration (paper-based vs. talking touchscreen), on a scale-by-scale basis using multiple-group factor analysis to compare in Mplus software (see Table 3 schematic below). All items will be treated as categorical indicators with response categories collapsed if there are fewer than five responses for a given response option.

Table 3: Schematic of multiple-group confirmatory factor analysis to be used on a scale-by-scale basis			
	Visit 1	Visit 2	Visit 3
Adequate health literacy	Factor loadings/ IRT parameters	Factor loadings/ IRT parameters	Factor loadings/ IRT parameters
Low health literacy	Factor loadings/ IRT parameters	Factor loadings/ IRT parameters	Factor loadings/ IRT parameters

We hypothesize that a metric invariable model will fit well for the talking touchscreen method. Acceptable fit will be defined as $CFI \geq .90$, $TLI \geq .90$, and $RMSEA \leq .10$. We hypothesize that unacceptable fit indices will be obtained for the paper-based testing. For descriptive statistics, we will report all fit indices produced by Mplus as well as factor loadings for each item. Longitudinal data will also be used to develop new longitudinal DIF tools in R, but these results will be considered exploratory until they can be tried and tested in other data sets.

Study Populations

The study population includes medical patients and community member, all might which complete questionnaires in other clinical and research contexts, ages 18 and older.

Study Variables

Demographics

All demographic variables are described in the protocol. We will report descriptive statistics of all demographics within language group as well as in total. We do not have specific hypotheses about demographics, but may conduct and report analyses of them, as well as presented additional analyses of demographics based on requests from manuscript reviewers.

Health literacy and numeracy

HealthLiTT and the NUMI will be used to determine health literacy groups using the above-described cutoffs. HealthLiTT is our main health literacy variable. All analyses of the NUMI are secondary.

Health questionnaires

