We hypothesize that DIF will be observed across adequate versus low levels of health literacy as measured by HealthLiTT.¹⁵ This hypothesis was formulated before any data were examined. In terms of direction, we predict that low-health-literacy groups will show lower item slopes. All questionnaires and subscales mentioned in the “Core battery for DIF Testing” section of protocol will undergo DIF testing. To examine DIF across health literacy status, we will conduct separate analyses within language and within testing format (paper-based vs. talking touchscreen). The overall N for these analyses, within strata, will be 304. We will use the *lordif* package in R for these analyses. This involves several steps. Four models are fit to the data (see Box 1). The models are regressions that link the probability of response type (e.g., “never”, “rarely”, “sometimes”, “often”, “always”) to a latent trait. If an item is free of DIF, then group (e.g., adequate vs. low health literacy) should have no effect. Thus, Model 2 and Model 3 should not fit significantly better than Model 1. It is well known that statistical significance is influenced, in part, by sample size. Thus, *lordif* uses effect-size measures to detect DIF, and to flag individual items where the effect of group exceeds a particular threshold. Effect sizes indicative of DIF will be chosen for each scale based on a Monte Carlo simulation carried out in *lordif*, which returns an effect size that would be unlikely given the null hypothesis of no DIF.

The following *a priori* decisions are important. We will use a Type I error rate of $\alpha = .01$ to generate the McFadden ΔR^2 effect size for each item that would be considered unusual if the null hypothesis of no DIF were true. Within each scale, we will select the smallest McFadden R^2 across all of the items. The minimum effect size we will consider

Box 1: Models fit by lordif

Model 0: $\text{logit}[P(Y \geq k)] = \alpha_k$
Model 1: $\text{logit}[P(Y \geq k)] = \alpha_k + \beta_1 (\text{ability})$
Model 2: $\text{logit}[P(Y \geq k)] = \alpha_k + \beta_1 (\text{ability}) + \beta_2 (\text{group})$
Model 3: $\text{logit}[P(Y \geq k)] = \alpha_k + \beta_1 (\text{ability}) + \beta_2 (\text{group}) + \beta_3 (\text{ability} \times \text{group})$

Note: α and β are logistic regression parameters. k refers to the number of thresholds needed for each item.

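### The SAP reads fewer flagged items on the touchscreen as evidence of reduced DIF, with no test or interval for the difference between modes

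*SAP*

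**What the plan says.** SAP, Study Design, describes the trial in these words: "This is a randomized experiment aimed at determining whether talking touchscreen technology can reduce DIF". The same sentence adds a second aim, a better testing experience.

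For the DIF aim, the SAP states three between-mode expectations:

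- **Flags.** Study Objectives says of the hypothesised reduction in test bias: "This will be evidenced by fewer items being flagged for DIF in the group that receives the talking touchscreen". The primary analysis section (DIF by health literacy) and the Meaning and Purpose section both repeat the fewer-items hypothesis.
- **Discrimination.** Among participants with low literacy, "we expect that the discrimination parameters of the touchscreen condition will be higher than the paper-based condition" (Study Objectives).
- **ΔR².** The primary analysis section expects larger values on paper for each DIF item. It does not say in which mode the item must have been flagged.

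The analysis is split by mode: "To examine DIF across health literacy status, we will conduct separate analyses within language and within testing format". The models in Box 1 contain ability, literacy group and their product, and no term for mode. The .01 error rate in that section sets the cut-off for flagging an item within a run.

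Study Timepoints adds two fit predictions: "We hypothesize that a metric invariable model will fit well for the talking touchscreen method", and "We hypothesize that unacceptable fit indices will be obtained for the paper-based testing". Each mode is held against fixed limits for CFI, TLI and RMSEA.

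**The concern.** A randomised comparison needs a statement about the difference between the arms. Here each arm gets its own DIF analysis and the reader compares two counts. The Overview sets a general standard, "All hypothesis testing will be carried out at a two-tailed Type I error rate of" .05, but the plan specifies no test of the mode difference in DIF across the battery for that level to govern.

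Two counts from noisy flagging procedures will often differ when nothing separates the modes. A surplus of one flagged item on paper would then be reported as reduced test bias. A real benefit would be reported with no measure of its uncertainty. The fit predictions have the same form: one mode passing a limit and the other failing it is not a test of the difference.

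**Working it through.** **1. The plan's own figures.** Two sites × 2 literacy levels × 2 sexes × 38 per mode = 304 per language-by-mode stratum, which agrees with "The overall N for these analyses, within strata, will be 304". The power section reports good fit in 90% of simulated runs at n = 100 per group; a re-run gave 89.2%. That figure concerns model fit. It gives neither power nor an error rate for the mode contrast.

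**2. Inputs.**

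- Item counts: 7 PROMIS scales of 8 (57-item Profile less one assumed pain-intensity item, split evenly), Meaning and Purpose 8, PHQ-9 9, RRS 10, PTSD checklist 20. Distinct items: 56 + 8 + 9 + 10 + 20 = 103.
- The SAP's list for DIF testing also names the two RRS subscales (5 items each assumed). Scales: 7 + 1 + 1 + 1 + 1 + 2 = 13 per language. The Berlin Questionnaire is left out because its item count is not given.
- Flag rate f: 1% is the SAP's per-item calibration under no DIF. Taking the smallest item cut-off in a scale makes this a lower bound unless the .001 floor binds. Rates of 5% and 10% are assumptions; they need some real DIF in both modes, which the SAP predicts.

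**3. Chance of fewer flags on the touchscreen when modes do not differ.** With independent Binomial(m, f) counts, P(touchscreen fewer) = (1 − P(tie))/2, where P(tie) is the sum of squared binomial probabilities. For m = 8, f = 1%: P(tie) = 0.857, so (1 − 0.857)/2 = 0.071.

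| Items m | f = 1% | f = 5% | f = 10% |
|---|---|---|---|
| 5 | 4.7% | 18.0% | 26.9% |
| 8 | 7.1% | 24.0% | 32.3% |
| 9 | 7.9% | 25.5% | 33.4% |
| 10 | 8.7% | 26.8% | 34.4% |
| 20 | 15.2% | 34.5% | 39.3% |
| 103 (pooled) | 34.8% | 43.6% | 45.4% |

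The same probabilities apply to paper having fewer flags.

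**4. Correlated flags within an 8-item scale** (beta-binomial, correlation 0.1 and 0.3): 5.5% and 3.7% at f = 1%; 21% and 16% at 5%; 31% and 26% at 10%.

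**5. Expected scales favouring the touchscreen by chance, per language.**

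- At 1%: 8 × 0.0715 + 0.0793 + 0.0869 + 0.1517 + 2 × 0.0467 = 0.98 of 13.
- At 10%: 8 × 0.3225 + 0.3341 + 0.3437 + 0.3928 + 2 × 0.2692 = 4.19 of 13.

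**6. Size of difference that chance explains.** Pooled at f = 10%, the SD of the difference in counts is √(2 × 103 × 0.1 × 0.9) = 4.3, and 1.96 × 4.3 = 8.4. About 8 items would be needed for a nominal two-sided .05. The stated rule accepts 1.

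**7. Cross-check.** A simulation in the style of lordif (13 scales of 8 graded items, ordinal logistic models, McFadden ΔR², simulated cut-off) gave 36% with no DIF and 42% with identical DIF in both modes at n = 304 per mode. At n = 182 it gave 40% and 43%.

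**8. Actual strata.** 728/4 = 182 on average, 60% of 304. If the 566 English speakers in the Meaning and Purpose section are within the 728, Spanish has (728 − 566)/2 = 81 per mode.

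**The case against.** Several objections have force.

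- **The randomised question has two halves.** A reader might infer that the trial has no inferential mode comparison at all. That is not so: the Exit Interview section correlates experience ratings with mode, gives 99% intervals, and calls a result significant if zero is excluded. The point is confined to DIF.
- **One scale has an interaction model.** The Meaning and Purpose analysis puts a Health LiTT by administration-type term on item slopes. It covers 8 items in English speakers, gives no error rate or interval for that term, and its hypothesis is again fewer items. It narrows the gap and does not close it.
- **The per-scale rule is not SAP text.** The SAP does not say whether counts are compared by scale or pooled, so both are shown. At the 1% calibration the per-scale figure is modest: 7%, or about 4% to 6% with correlated flags, against 2.5% for the favourable side of a two-sided .05 test.
- **The rule is not tilted.** A reader might infer a bias towards the touchscreen. Chance favours paper just as often, and such results would be visible too.
- **The ΔR² comparison is not shown to be biased.** Choosing items because they were flagged on paper would tilt it against paper; choosing those flagged in either mode would not. The SAP does not say which, so no error rate can be assigned. Nor can one be given for the fit predictions, since no pass rate is stated.
- **Effect sizes are a deliberate choice.** The SAP notes that significance depends on sample size. That justifies judging items by magnitude, but a magnitude compared between arms still needs an interval.

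**Conclusion.** The concern holds for the DIF half of the randomised question. The SAP has a stated evidential rule that a one-item chance difference satisfies, and no test or interval for the mode difference in flags, ΔR² or discrimination across the battery.

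Under no mode effect, the chance of a touchscreen-favouring count runs from about 4% (one 8-item scale, 1% flag rate, correlated flags) to 45% (all items pooled, 10% flag rate). About 1.0 of 13 scales per language at 1%, and 4.2 at 10%, would favour the touchscreen by chance.

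The figures rest on the assumed item split, on flag rates above 1% that the documents do not give, and, outside the correlated-flag and simulation checks, on independent flags. The absence of a between-mode contrast does not depend on any of these. It should be fixed before the mode conclusion is drawn.

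**What to change.** Within each language, base the mode conclusion on a direct contrast, paper minus touchscreen:

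1. Take the difference in mean ΔR² over all items, and the difference in flag counts, with one common cut-off in both modes. Do not choose items for the ΔR² comparison on paper flags alone. If the 50% re-run rule fires in one mode, raise the cut-off in both.
2. Give a two-sided 95% interval from a bootstrap of participants, and a p-value from permuting mode labels within literacy group. The permutation matters where mode sizes differ, because ΔR² cannot be negative and tends to be larger in smaller samples.
3. Claim reduced DIF only if the interval excludes zero in favour of the touchscreen.
4. State whether the claim is pooled or per scale; if per scale, apply Holm over scales.
5. Report separate-mode flag counts and the fit verdicts under Study Timepoints as descriptive.
6. The literacy by mode model planned for Meaning and Purpose may be extended to other scales as supporting analysis where it can be estimated.

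**Cost.** SAP wording and computing time, and fewer chance successes to report. Intervals will be wide: strata average 182 rather than 304, and Spanish may have only about 81 per mode. If mode results have already been seen, the SAP's own rule on analyses that were not pre-registered requires the contrast to be labelled post-hoc.

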Using a large sample, we will determine the psychometric properties of health questionnaires across levels of health literacy. Testing will be conducted in English and Spanish, across two modes of administration (paper-and-pencil vs. talking touchscreen). Each participant will have three visits (baseline, 3-month, and 6-month follow-up), described below, in order to determine changes in psychometric properties over time. We will use *differential item functioning* (DIF) and other psychometric analyses to identify questionnaire items with varying characteristics across levels of health literacy. Before the COVID-19 pandemic, our original plan was to recruit $N = 1216$ participants for in-person assessments. At the time of this plan our final N is 728 participants who have completed a health literacy assessment; some of these participants are missing data on subsequent questionnaires. In-person recruitment was put on hold during the COVID-19 pandemic; in order to adapt the the pandemic, a subset of participants ($N = 304$) was invited to a phone-based protocol that included data collection about the impact of COVID-19, vaccine confidence, and health-related quality-of-life (PROMIS-29 profile).

- **Develop alternative modes of test administration that can better accommodate people with low health literacy.** National statistics indicate that 14% of adults in the United States have below basic reading skills, and over 75 million Americans have below basic or basic health literacy skills.¹⁴ These data strongly indicate that many individuals seeking health care will have difficulties with written questionnaires, even those that have been carefully developed such as those in the NIH PROMIS. We will test an alternative mode of administration that has been specifically designed to aid people of low health literacy – a computer-assisted “talking” version that uses speech technology that participants can privately access as needed to have items and response options

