304 English speaking 152 with low health literacy 76 women g1 38 randomized to paper-based 19 Order 1 19 Order 2 38 randomized to talking touchscreen 19 Order 1 19 Order 2 76 men g2 38 randomized to paper-based 19 Order 1 19 Order 2 38 randomized to talking touchscreen 19 Order 1 19 Order 2 152 with adequate health literacy 76 women g3 38 randomized to paper-based 19 Order 1 19 Order 2 38 randomized talking touchscreen 19 Order 1 19 Order 2 76 men g4 38 randomized to paper-based 19 Order 1 19 Order 2 38 randomized talking touchscreen 19 Order 1 19 Order 2	304 Spanish speaking 152 with low health literacy 76 women g5 38 randomized to paper-based 19 Order 1 19 Order 2 38 randomized to talking touchscreen 19 Order 1 19 Order 2 76 men g6 38 randomized to paper-based 19 Order 1 19 Order 2 38 randomized to talking touchscreen 19 Order 1 19 Order 2 152 with adequate health literacy 76 women g7 38 randomized to paper-based 19 Order 1 19 Order 2 38 randomized talking touchscreen 19 Order 1 19 Order 2 76 men g8 38 randomized to paper-based 19 Order 1 19 Order 2 38 randomized talking touchscreen 19 Order 1 19 Order 2	304 English speaking 152 with low health literacy 76 women g9 38 randomized to paper-based 19 Order 1 19 Order 2 38 randomized to talking touchscreen 19 Order 1 19 Order 2 76 men g10 38 randomized to paper-based 19 Order 1 19 Order 2 38 randomized to talking touchscreen 19 Order 1 19 Order 2 152 with adequate health literacy 76 women g11 38 randomized to paper-based 19 Order 1 19 Order 2 38 randomized to talking touchscreen 19 Order 1 19 Order 2 76 men g12 38 randomized to paper-based 19 Order 1 19 Order 2 38 randomized to talking touchscreen 19 Order 1 19 Order 2	304 Spanish speaking 152 with low health literacy 76 women g13 38 randomized to paper-based 19 Order 1 19 Order 2 38 randomized to talking touchscreen 19 Order 1 19 Order 2 76 men g14 38 randomized to paper-based 19 Order 1 19 Order 2 38 randomized to talking touchscreen 19 Order 1 19 Order 2 152 with adequate health literacy 76 women g15 38 randomized to paper-based 19 Order 1 19 Order 2 38 randomized to talking touchscreen 19 Order 1 19 Order 2 76 men g16 38 randomized to paper-based 19 Order 1 19 Order 2 38 randomized to talking touchscreen 19 Order 1 19 Order 2

Study Timepoints

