The literature exploring the relationship between overall vaccine hesitancy (not specific to COVID-19 vaccine) has also found conflicting directional relationships between vaccine hesitancy and educational status. Although some studies have found greater vaccine refusal or hesitancy in lower education groups,^{44, 45} others have not.⁴⁶ The relationship between health literacy and vaccine views is also not clear, with studies finding conflicting results.⁴⁷ Health literacy is a potential modifiable factor for vulnerable populations with uncertain vaccination views. We seek to explore the relationship between COVID-19 vaccine hesitancy and health literacy in a diverse participant sample of $N = 300$, who are a subset of the parent study.

Hypothesis: We hypothesize that health literacy is a mediator of the relationship between race/ethnicity and vaccine confidence, such that race predicts health literacy, which is in turn inversely associated with vaccine confidence. Using mediation analysis, we will determine how much of the effect of race/ethnicity on vaccine confidence is mediated by health literacy (i.e., the indirect effect) while also estimating the direct and total effect. A sample of 300 participants will be included in this baseline analysis exploring the relationship between race/ethnicity, health literacy (measured by Health LiTT⁴⁸ obtained at the baseline of the parent study), and the VCI which was administered at follow-up during a period of COVID-19 vaccine approval and early administration. This hypothesis was formulated before looking at any of the data from the phone-based protocol.

Measures:

Demographic Covariates

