2. Determine whether health literacy mediates the relationship between baseline demographics (e.g., education, age, gender) and future stress-related symptoms using the PCL-5. Will run separate models for English and Spanish.
3. Determine which aspects of health-related quality of life (measured by PROMIS-57 Profile v2.1, which includes Physical Function, Anxiety, Depression, Fatigue, Sleep Disturbance, Ability to Participate in Social Roles and Activities, Pain interference, and Pain Intensity) are associated with trauma symptoms measured by the PCL-5, after statistically controlling for demographics and health literacy.

Hypotheses:

1. There will be a significant association between health literacy (measured by Health LiTT) and the PCL-5 scale, such that lower health literacy will be associated with higher trauma-related symptoms.
2. Health literacy serves as a mediator between baseline demographics (education, age, gender, ethnicity) and future stress related symptoms as per the PCL-5.
3. Higher levels of self-reported anxiety, depression, and ability to participate in social roles and activities from the PROMIS-57 will be associated with higher PCL scores.

Data Description

Datasets used

NIH-funded Reducing Assessment Barriers for Patients with Low Health Literacy dataset, also known as the DIF study (PI: [name]). All timepoints will be analyzed for this project (baseline, 3-month, and 6-month time points). The dataset is not publicly available. The data are not public, but will be made available to us from the DIF team at the time of publication.

Data Collection Procedures (from parent study)

Participants included those who were aged 18 or older, could provide informed consent, were open to randomization for mode of administration, were willing to complete questionnaires, fluent in English and/or Spanish, willing to attend three face-to-face sessions, and did not have plans to move outside of the study area for six months. Study participants were recruited from two sites: Northwestern University (Chicago, IL) and Boston Medical Center (Boston, MA). Participants were ineligible for the study if they had significant cognitive

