# The model will have a form similar to the R code below:  
# Note: race and ethnicity will be analyzed in English-speaking participants  
model <- lm(posttraumatic_stress ~ Health_LiTT + education + age + gender + race, data = data)  
summary(model)
```

The results will be evaluated by examining the magnitude and 95% confidence intervals for health literacy, as measured by Health LiTT. We will use “non-Hispanic white” as the reference category, and all other categories will be binary coded (0/1).

For Aim 1, the statistical analysis will involve a multiple linear regression model to explore how various factors such as health literacy (as measured by the Health LiTT test) and demographics such as education, age, gender, race, and ethnicity predict levels of posttraumatic stress (as per the PCL-5). The linear regression model will estimate the relationships between these variables. This will also include the calculation of coefficient estimates, confidence intervals, and significance levels. We will also explore assumptions of linear regression such as linearity, homoscedasticity, normality of residuals, and multicollinearity. We will assess all these aspects to ensure that there is no individual data point that disproportionately impacts results. For ethnicity, “non-Hispanic white” will serve as the reference group, and other ethnic categories will be binary coded (0/1; 0 for not belonging to this category and 1 for belonging to it). The results will be evaluated by examining the magnitude and 95% confidence intervals for health literacy, as measured by Health LiTT. We will also evaluate model goodness-of-fit (via R-squared statistic) to understand more about how well the model explains any variability in posttraumatic stress. We may explore interaction terms and model comparison as needed.

Aim 2 example code:

```

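### Recruitment was planned at 50% low health literacy within each gender, so the gender-to-Health LiTT path in the PCL-5 mediation (Aim 2) depends partly on recruitment and is not an unbiased population estimate

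*SAP*

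**What the plan says.** **Sampling.** SAP, Study Design, Table 2 stratifies by site, language, health literacy and gender. The first low-literacy cell reads "152 with low health literacy 76 women g1 38 randomized to paper-based". Its adequate-literacy counterpart is "152 with adequate health literacy 76 women g3 38 randomized". The Spanish column repeats the pattern: "304 Spanish speaking 152 with low health literacy 76 women g5". The SAP presents Table 2 as the design before the pandemic and adds that "we were unable to recruit all 1216 participants". Study Objectives gives the outcome: "At the time of this plan our final N is 728 participants who have completed a health literacy assessment". The opening section says screening data were analysed as predictors of health literacy so that participants could be stratified better. The cutoff is a Health LiTT T score of 55.

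**PCL-5 mediation.** In the SAP section on health literacy as a possible mediator for stress and trauma symptoms, Hypothesis 2 states: "Health literacy serves as a mediator between baseline demographics (education, age, gender, ethnicity) and future stress related symptoms as per the PCL-5". The Aim 2 code regresses Health LiTT on education, age, gender (path a3) and race. The Aim 2 text adds language to the mediated demographics, yet fits separate English and Spanish models. An indirect effect counts as significant when its 95% bootstrap interval excludes zero.

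**Vaccine mediation.** The Vaccine Confidence addendum says "we will determine how much of the effect of race/ethnicity on vaccine confidence is mediated by health literacy". It uses a Hispanic dummy (X2) against non-Hispanic white participants, describes no split by testing language, and treats gender as a covariate.

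Neither section mentions literacy-stratified recruitment, sampling weights or selection on the mediator. The limitations in the vaccine addendum cover generalisability, confounding or collider bias, and measurement error, but not this.

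**The concern.** Health LiTT is both a variable on which recruitment was balanced and, in these analyses, the mediator. Balancing it within gender pulls the average literacy of women and men together in the sample, whatever the gap in the source population. The first leg of the gender pathway (a3) is then partly a product of the recruitment targets, and so is the product a3 × b. A small gender indirect effect, or an interval covering zero, would be read as showing that health literacy does not carry the gender difference in trauma symptoms. Part of that result could come from the sampling. If cells filled unevenly, the error could go the other way and produce an apparent pathway.

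**Working it through.** **1. Reproduce Table 2.** Each group is 19 × 2 orders × 2 modes = 76. Four groups give 304 per language and site, and 16 × 76 = 1216, the SAP's planned total. In every gender × language × site block the low share is 76 / (76 + 76) = 50%.

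**2. How far the table was filled.**
- Overall: 728 / 1216 = 59.9%.
- English: Meaning and Purpose Analyses counts 566 English speakers at baseline through March 2020, against 2 × 304 = 608 planned, or 93%.
- Spanish: if all 566 are among the 728, at most 728 − 566 = 162 were Spanish speakers, or 27% of 608.

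Achieved counts by literacy and gender are not given.

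**3. Quotas met on Health LiTT itself.** Assumptions not in the documents: T scores normal with SD 10, and gender means centred on 45 to 60. With z = (55 − μ)/10:
- mean of the low group = μ − 10 φ(z)/Φ(z)
- mean of the adequate group = μ + 10 φ(z)/(1 − Φ(z))
- quota mean = half of each

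Example, a true gap of 3 centred on 55. For μ = 56.5 the group means are 47.54 and 63.55, average 55.55. For μ = 53.5 they are 46.45 and 62.46, average 54.45. The gap is about 1.1, or 36% of 3.

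| Centre | True gap 2 | True gap 3 | True gap 5 | Retained |
|---|---|---|---|---|
| 45 | 0.83 | 1.24 | 2.07 | 41% |
| 50 | 0.75 | 1.13 | 1.89 | 38% |
| 55 | 0.73 | 1.09 | 1.82 | 36% |
| 60 | 0.75 | 1.13 | 1.89 | 38% |

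**4. Quotas met on a proxy.** If recruitment was balanced on a screening measure with correlation r to Health LiTT, and gender acts on the proxy only through Health LiTT, the fraction retained is 1 − r²(1 − k), where k is the fraction from step 3. With k = 0.36:
- r = 0.3: 1 − 0.09 × 0.64 = 94%
- r = 0.4: 1 − 0.16 × 0.64 = 90%
- r = 0.5: 1 − 0.25 × 0.64 = 84%
- r = 0.7: 1 − 0.49 × 0.64 = 69%

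The documents give no value for r.

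**5. Uneven filling, no true gap.** The apparent gap is the difference in low share times the distance between the adequate and low means. That distance is 16.0 T points at centre 55 (62.98 − 47.02) and 18.1 at centre 45 (60.25 − 42.12). With 45% against 55% low, the gap is 0.10 × 16.0 = 1.6 to 0.10 × 18.1 = 1.8 points.

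**6. Carry-through to the indirect effect.** In an illustrative simulation with full quotas, fitted separately by language and adjusted for education, the gender path fell from 1.99 to 0.86 in English and from 1.97 to 0.93 in Spanish. In the pooled fit the literacy-to-outcome path b stayed at 0.030, so a × b shrank in proportion: 0.060 to 0.028 for gender.

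**7. Language in Aim 2.** Within an English-only or Spanish-only model, language is constant. It has no a-path there, so no indirect effect can be formed. This needs no assumption.

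**The case against.** The strongest reply is that Table 2 is an unfinished target. The SAP shows no achieved cells, no cap and no rule for turning people away once a cell was full. Eligibility has no literacy criterion, and Health LiTT is administered at Visit 1 after consent. Only the single-item screener and demographics could have steered recruitment, and selection on a proxy attenuates less (step 4). The PCL-5 work is also a late addition that appears to sit under the exploratory heading, and the vaccine limitations already warn about generalisability.

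Most of this stands, and it rules out 36-41% as the expected loss. It does not remove the problem. The SAP's own account of using screening data to improve stratification shows that recruitment was steered by expected literacy. The English cells were close to full in total. Partial or uneven filling leaves the path dependent on recruitment, with the direction unknown.

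A reader might go further and infer that the mediation analyses cannot estimate the gender or Hispanic pathways at all. The documents do not support that. Health LiTT is continuous, so part of any mean difference survives; the issue is bias. Ethnicity is not a stratification variable; language is. The vaccine X2 path could be affected through language, but any specific size would have to assume a 50/50 literacy split among Spanish-tested participants, and at most about 27% of the planned Spanish sample can have been recruited. In the PCL-5 models the language split removes that route, and a note in the Aim 1 code says "race and ethnicity will be analyzed in English-speaking participants". In the vaccine model gender is only a covariate.

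**Conclusion.** The point holds for the gender path in PCL-5 Aim 2 / Hypothesis 2. By plan, literacy was balanced within gender, so a3 and the gender indirect effect depend partly on recruitment and are not unbiased for the population. It applies most plausibly in the English model.

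The size is not determined by the documents. It ranges from 36-41% of a true gap retained (quotas met on Health LiTT; normal scores, SD 10, means 45-60) to about 94% retained (proxy with r = 0.3). A spurious gap of 1.6-1.8 T points is possible if cells filled at 45% against 55% low. For the vaccine X2 path, a possible distortion through language should be acknowledged, but no figure can be defended. Separately, listing language as mediated in language-split models is an internal inconsistency. The primary DIF analyses are not touched by this point.

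**What to change.** 1. In PCL-5 Aim 2 / Hypothesis 2, remove gender from the tested indirect effects. Keep it as a covariate with its direct effect, and say that its path to Health LiTT was subject to the Table 2 targets.
2. Remove language from the mediated demographics in Aim 2.
3. Report achieved low and adequate counts by gender, language and race/ethnicity, so readers can judge how far the targets took effect.
4. In both mediation sections, state that a-paths, indirect effects and any proportion mediated are specific to a literacy-stratified sample. Add this to the vaccine limitations.
5. Leave the primary X2 analysis in both languages. Restricting it to English-tested participants would drop the Spanish-tested Hispanic participants and change what is estimated. At most, add it as a sensitivity analysis.

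The cost is a few lines of SAP text and one table from data already held. The downside is that the gender indirect effect is no longer tested.
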